## **9.6 Safety Extension (Week 12 to Week 24)**

From Week 12 to Week 24, all patients will receive ricolinostat 120 mg daily. Patients will return to the clinic as outlined in the schedule of events and at each visit procedures specified in the schedule of events for that visit will be performed.

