### **9.6.1 Week 12**

The following procedures will be performed at Week 12:

- Administer C-SSRS (Since Last Visit version);
- Obtain vital signs (temperature, respiration rate, pulse, and blood pressure) while patient is sitting after a minimum 5-minute rest. Standing pulse and blood pressure to be obtained following sitting vital signs;
- Perform directed physical exam to assess changes from the prior visit or new concerns;
- Assess skin integrity and wound healing, if applicable;
- Perform 12-lead ECG (after the patient has been resting in the supine position);
- Collect blood samples for the following:

- Fasting chemistry (fasting of 8-10 hours), hematology, and HbA1c;
- Collect urine samples for the following:
  - Urinalysis;
  - Urine pregnancy test (if FOCBP);
  - Urine drug screen (performed at the discretion of the Investigator);
- Administer BPI-SF (pain interference section only);
- Administer NTSS-6;
- Perform UENS;
- Administer Norfolk Diabetic QOL-DN;
- Administer PGIC;
- Record concomitant medications and AEs;
- Collect returned study drug (used and unused bottles) and perform study drug accountability;
- Instruct patient on daily completion of NRS (worst and average pain experienced each day) and rescue medication use, as applicable (at the discretion of the Investigator); and
- Dispense study drug assigned by IRT.

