#### **10.3.7 Safety Analyses**

AEs will be coded using the Medical Dictionary for Regulatory Activities (MedDRA) by System Organ Class (SOC) and preferred term (PT). Only treatment-emergent AEs (TEAEs) will be

included in summary tables. A TEAE is defined as any AE that occurs after the start of study drug or was present at baseline and worsened after taking study drug.

The number and percent of patients with at least one 1) AE, 2) severe AE, 3) SAE, 4) AE leading to discontinuation, and 5) treatment-related AE will be presented by treatment arm for the Safety Population. The number and percent of patients with AEs will be presented by MedDRA SOC and PT for each treatment arm and overall. AEs will also be summarized by PT; by SOC, PT, and severity; and by SOC, PT, and relationship to study treatment. SAEs and AEs leading to discontinuation will also be presented.

The counts and percentages for AE summary tables will be based on the Safety Population. Patients with multiple unique events will be counted once per each unique PT and each unique SOC. If a patient has more than one AE that is coded to the same PT, the patient will be counted only once (using the maximum severity assigned) for that PT.

Observed values and change from baseline will be presented by visit and treatment group for hematology and chemistry laboratory tests. The number and percent of patients with hematology, chemistry, and urinalysis results outside the normal range will be presented by visit for each treatment arm. A second table will present shifts with respect to the lower limit of normal; the table will be repeated for shifts with respect to the ULN. Laboratory tests with categorical results that cannot be analyzed by change from baseline or shift table analysis will not be included in these summaries, but will be listed. Another table will present findings of special interest, including selected hematology and serum chemistry abnormalities relevant to the assessment of safety.

Descriptive statistics for vital signs and ECG results will be presented by treatment group.

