#### 6.1.2. Analysis populations

The following populations are planned:

- Pre-randomized safety population (pSAF): All patients who have at least one observation during the pain observation period (day -14 to day -1/pre-treatment) and who were not randomized.
- Safety population (SAF): All patients who been randomized and received at least one dose of study drug
- Intent to treat (ITT) population: All patients randomized regardless of study drug administration
- Full analysis set (FAS) population: All patients who receive at least one dose of study drug, have a baseline average NRS score and, have at least one post-baseline average NRS score.
- Per-protocol population (PPP): All patients in the FAS population who have no major protocol violations, a valid baseline value of the NRS, meet all inclusion/exclusion criteria, missing no more than 2 weeks of diary data, and have a mean compliance rate of at least 60% (i.e., on average provide ratings on 4 or more days of each week).

6.1.3. *General considerations*

When presented, listings will be presented by patient number, treatment group, and measurement time.

In all analyses, the same number of decimal places as in the raw data will be presented for point estimates and univariate analysis. One more decimal place than in the raw data will be presented when reporting mean and standard deviation.

Continuous variables will be summarized by treatment group using descriptive statistics (n, mean, median, standard deviation, minimum, and maximum). For categorical variables, frequencies and percentages will be presented by treatment. The denominator for all categorical variables is the number of randomized patients.

All statistical testing will be based on a two-sided significance level of 0.05 unless otherwise stated.

*Baseline* is defined as the last observation prior to initiation of study medication.

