Baseline assessment for the NRS is expected to be the mean of the values collected during the 5-9 days that 1) follow the training visit follow-up assessment at the end of the first week of the pain observation phase and 2) immediately precede randomization (i.e., prior to the initial study drug dose administration). Should this value be unavailable (for example, if less than 5 days were present between the training visit follow-up visit and randomization) or should the timing of the evaluation in relation to the first administration of study drug not be determinable (e.g., missing time for baseline assessment or missing time value for study drug administration) then the mean of the 5 days of the NRS ratings closest to and before randomization will be selected as the baseline value. Instead of relying solely on visit labels in the clinical database for post-baseline values, results collected at a particular time will be attributed to a specific time point by calculating the time relative to randomization.

For all other assessments, the baseline assessment is the last value for that assessment collected prior to randomization and the first administration of study drug.

For visits (or events) that occur on or after randomization, study day is defined as:

$$\text{Study day} = \text{date of event} - \text{randomization date} + 1$$

For visits (or events) that occur before randomization, study day is defined as:

$$\text{Study day} = \text{date of event} - \text{randomization date}$$

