## 11. Safety analyses

All safety analyses will be performed using the safety population. Safety and tolerability will be assessed by clinical review of all safety parameters including AEs, laboratory values, and vital signs. The safety analyses will include all results collected from randomization through the end of the study. All safety presentations will be presented by treatment group ( 180µg, 120µg, and placebo).

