### **11.2. Clinical laboratory evaluations**

Each laboratory value and change from baseline (when appropriate) will be summarized in tables and figures for hematology, blood chemistry and urinalysis for each treatment at Screening, discharge, and end of study. Boxplots of laboratory values will be provided. Shift tables may also be provided.

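### With only a pre-randomisation baseline, hematology and chemistry change after Week 12 in patients switched from placebo does not estimate change on ricolinostat

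*SAP*

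**What the plan says.** SAP section 6.1.3 defines baseline in general as a value that "is defined as the last observation prior to initiation of study medication". For all assessments other than the pain score it is more specific: "the baseline assessment is the last value for that assessment collected prior to randomization and the first administration of study drug". Neither document defines a Week 12, pre-switch or open-label baseline.

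The treatment changes partway through the period covered. Protocol section 9.6 states: "From Week 12 to Week 24, all patients will receive ricolinostat 120 mg daily". SAP section 11 nevertheless treats the study as one span: "The safety analyses will include all results collected from randomization through the end of the study". It adds: "All safety presentations will be presented by treatment group".

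For laboratory tests, Protocol section 10.3.7 plans: "Observed values and change from baseline will be presented by visit and treatment group for hematology and chemistry laboratory tests". It also plans shift tables against the limits of normal. SAP section 11.2 says: "Each laboratory value and change from baseline (when appropriate) will be summarized in tables and figures". It makes shift tables optional and names three occasions: screening, discharge and study end.

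The Week 12 visit (Protocol section 9.6.1) includes "Fasting chemistry (fasting of 8-10 hours), hematology, and HbA1c", as well as ECG, vital signs and urinalysis. Dispensing of study drug is the last item listed.

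**The concern.** The open-label extension exists to extend the safety and tolerability assessment (Protocol section 7.2), and safety is part of the primary objective (SAP section 2.1). Patients who move from placebo to ricolinostat contribute a measurement just before first exposure and further measurements during it. A reader of an extension table would expect the change shown for them to be change since starting the drug.

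Under the single baseline it is not. A cell count that fell during the 12 weeks on placebo appears at Weeks 14 to 24 as a fall in patients taking ricolinostat. A count that rose on placebo and fell back on ricolinostat appears as no change. The same holds for a patient's category in a shift table.

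**Working it through.** **1. How many patients.** The sample size inputs are a difference of 0.8, SD 2.35, two-sided alpha 0.05 and power 0.80 (SAP sections 6.1.1 and 6.1.3). The effect size is 0.8 / 2.35 = 0.340. The normal approximation gives 2 × (1.960 + 0.842)² / 0.340² ≈ 136 per arm, 272 in total. The two-sample t-test gives 136.4, rounded up to 137 per arm, 274 in total, which reproduces the plan's figure. With 1:1 randomisation, up to about 137 patients can switch. The documents give no dropout rate. If 10% to 30% left before Week 12 (an assumption), 0.9 × 137 ≈ 123 to 0.7 × 137 ≈ 96 would switch.

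**2. What the planned change contains.** For a placebo-randomised patient write d1 = (Week 12 − pre-randomisation) and d2 = (Week 24 − Week 12). Then

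Week 24 − pre-randomisation = d1 + d2.

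Here d1 arises entirely on placebo and d2 on ricolinostat. This is an identity and needs no assumption. If the tabulated figure is read as change since starting ricolinostat, the error is exactly d1, whatever the sample size. At Week 28 a third term is added, the change after dosing stops at Week 24.

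**3. Which output is affected.** After Week 12, Table 1 of the protocol schedules hematology at Weeks 14, 18, 24 and 28, and chemistry at Weeks 24 and 28. Three things are not affected:
- changes up to Week 12 in either arm;
- the ricolinostat arm's change over 24 weeks, which is all on drug;
- the first database lock, which leaves out data after Week 12 (SAP section 5.1).

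**4. Illustration (assumed values).** The documents give no drift. Taking hemoglobin changes in g/dL:

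| d1 on placebo | d2 on ricolinostat | Change from pre-randomisation | Change from Week 12 |
|---|---|---|---|
| −0.3 | 0 | −0.3 | 0 |
| 0 | −0.3 | −0.3 | −0.3 |
| +0.3 | −0.3 | 0 | −0.3 |
| 0 | 0 | 0 | 0 |

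The first row shows a fall that did not occur on the drug. The third hides one that did.

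For individual falls of more than 2 g/dL, assume no drug effect and a normal change with SD 0.7 to 1.0:
- No placebo drift: Φ(−2/0.7) = 0.2% to Φ(−2/1.0) = 2.3%, the same for both baselines if the SD is the same.
- Placebo drift −0.3: Φ(−1.7/0.7) = 0.8% to Φ(−1.7/1.0) = 4.5% with the pre-randomisation baseline, still 0.2% to 2.3% with Week 12.
- In 137 patients that is about 1.0 to 6.1 patients rather than 0.3 to 3.1.

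These figures show direction and scale. They are not predictions.

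**5. What a Week 12 reference does not remove.** d2 is itself the drug effect plus any change over Weeks 12 to 24 that would have happened anyway. No patient is on placebo then, so the two parts cannot be separated. If the drift of −0.3 continued at the same rate, the Week 12-referenced change would still show −0.3 with no drug effect.

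**The case against.** A single pre-randomisation baseline is a common convention. It keeps the two randomised arms on the same footing at Week 24, shows the cumulative change from the pre-study value, and is broadly in line with the protocol's monitoring rules for events of special interest, which also use pre-treatment values (sections 11.10.2.2 and 11.10.2.2.1). This stands, and it is the reason to add a second baseline rather than replace the first.

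The by-visit tables in Protocol section 10.3.7 would let a reader subtract the Week 12 mean from the Week 24 mean. That works roughly for means, but dropout changes the denominators and patient-level shifts cannot be recovered. SAP section 11.2 names no Week 12 column, and the SAP governs where the two differ (SAP section 1).

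Output by randomised group already keeps switchers in a column of their own. This also stands: separating the groups is largely a matter of labelling. It does not change what the entries measure.

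A reader might infer that every safety measure is affected. The documents do not support that. Protocol section 10.3.7 plans only descriptive statistics for vital signs and ECG. SAP sections 11.4 and 11.5 plan change for them, but at hours after a dose, not at Weeks 14 to 28. The clearly planned output concerned is hematology and chemistry.

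A reader might also take Week 12 to be a clean baseline. Without a concurrent control it is not, as step 5 shows. Nor do the documents say outright, as they do for Day 1, that the Week 12 assessments precede the next dose. The order of the visit list only implies it.

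**Conclusion.** The point holds for placebo-randomised patients after Week 12, in hematology and chemistry change from baseline and any shift tables. Those summaries combine change on placebo with change on ricolinostat and do not estimate change on drug. This follows from the baseline definition and the switch alone.

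Its size is unknown. It reaches up to about 137 patients before dropout, and the error in the mean equals the mean placebo-period change, which could be near zero. The hemoglobin figures rest on an assumed drift and assumed SDs.

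It would be wrong to conclude that the trial's safety conclusions are unsound. The randomised comparison to Week 12 and the ricolinostat arm's 24-week change use a suitable baseline, and the planned laboratory summaries are descriptive, so no test is distorted. This is a low-cost improvement to the extension-period reporting.

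**What to change.** Keep the pre-randomisation baseline for all patients. In SAP sections 6.1.3 and 11.2 add text such as: *For patients randomised to placebo, a second safety baseline is the last value before the first dose of open-label ricolinostat, normally from the Week 12 visit. Laboratory change and shift summaries after Week 12 will be shown against this baseline as well as against the pre-randomisation baseline.*

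- Label the extension columns placebo-to-ricolinostat and ricolinostat-to-ricolinostat.
- List the actual extension visits for laboratory summaries in section 11.2.
- If extension-period change in ECG or vital signs is summarised, treat it the same way.
- State beside the tables that these within-patient changes have no concurrent control.
- Derive the second baseline from the date of the first open-label dose, not from the Week 12 window in SAP Exhibit 4. That window is set at 14 to 32 days after the last dose and cannot capture the visit of a patient who continues dosing.
- Leave the protocol's monitoring baselines for events of special interest as they are.

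The cost is one extra baseline flag and a second set of extension tables, with no new data and no effect on sample size or the primary analysis. Settle it before the first unblinding, so that the choice is made without sight of treatment results.

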#### 6.1.4. *Visit windows*

Analysis visits and their windows are defined using derived study day (Section 6.1.3) instead of relying on visit labels in the clinical database because clinical visits may occur outside protocol-specified windows. Study day and days after last dose are calculated using the actual date of each scheduled and unscheduled assessment and compared to the target for each analysis visit as specified in Exhibit 4.

If a parameter is assessed or measured more than once within a visit window, the one that is closest to the protocol-scheduled time point (i.e., target) is used for the purposes of data analysis and summary. If two assessments are equidistant from a target, the earlier assessment is used. If the visit used for analysis includes two assessments on the same day, the average of the two measurements is used.

Records from visits not closest to the target study day, and therefore not used in analyses, are presented in by-subject data listings.

**Exhibit 4. Example of study days and analysis timepoints**

Analysis visit	Label	Study day a	Analysis window
0	Day 1 b	1	1
1	Week 1	5	2 ≤ study day ≤ 9
2	Week 2	14	10 ≤ study day ≤ 18
4	Week 4	28	24 ≤ study day ≤ 32
8	Week 8 c	56	52 ≤ study day ≤ 60
12	Week 12 d	84	14 ≤ days after last dose ≤ 32
14	Week 14	98	94 ≤ study day ≤ 102
18	Week 18	126	122 ≤ study day ≤ 130
24	Week 24 e	168	164 ≤ study day ≤ 172
26	Week 26 f	182	14 ≤ days after last dose ≤ 32
28	Week 28	196	192 ≤ study day ≤ 200

a) Study Day is relative to the date of randomization (Section 6.1.3).

b) Day 1 is the last measurement prior to the first study drug administration.

c) Week 8 is the end of the double-blind, placebo-controlled treatment period.

d) Week 12 is the start of the open-label safety extension period.

e) Week 24 is the end of the open-label safety extension period.

f) Week 26 is the start of the follow-up period.

*6.1.5. Procedures for handling missing data*

*6.1.5.1. Missing data on the primary efficacy endpoint*

The primary efficacy endpoint (e.g., NRS) is captured in a daily log. Missing daily NRS entries will be handled by performing a simple weekly average of the daily scores so long as four or more entries occur during the week. If three or fewer entries occur during the week, then the scores' weekly average will be set to missing for that week. Missing values will be multiple imputed using missing at random multiple imputation for intermittent missing values and reference-based imputation for all other missing data. These data will be part of the blinded data review with the option to change the approach to the summary score during the blinded data review process.

*6.1.5.2. Missing UENS*

The key secondary endpoint will be analyzed using missing at random imputation for intermittent missing data and reference-based imputation for all other missing data.

*6.1.5.3. Missing data for secondary endpoint*

Missing values for secondary endpoints will not be imputed. All results will be analyzed under the complete case scenario.

*6.1.5.4. Missing or partial stop- or start-dates for adverse events*

Missing or partial stop- or start-dates for adverse events will be imputed using the most conservative (e.g., worst case scenario) assumption. In all cases of missing or partial information, the site will be instructed to attempt to obtain the missing details. The rules for imputation follow:

- If the starting day is missing, then the day will be imputed to the 1st of the month unless the starting month is the same as the randomization month.
- If the starting day is missing and the starting month is the same as the randomization month, then the starting day will be imputed to the randomization day and the event will be assumed to be treatment emergent.
- If the starting month or year is missing, then the starting date will be imputed to the randomization date and the event will be assumed to be treatment emergent.
- If the end day is missing, then the end day will be imputed to be the last day of the month.
- If the end month is missing and the end year is the same as the study termination year, then the event date will be set to missing and the event will be assumed to be “on going” at time of study termination.
- If the end month is missing and the end year is before the year of study termination, then the end date will be imputed to the last day of the year (31DECXX).

*6.1.5.5. Missing or partial stop- or start-dates for concomitant medications*

Missing or partial stop- or start-dates for concomitant medications will be imputed using the most conservative (e.g., worst case scenario) assumption. Study sites will be instructed to

attempt to obtain the missing details in all cases of missing or partial information. The rules for imputation follow:

- If the starting day is missing, then the day will be imputed to the 1st of the month unless the starting month is the same as the randomization month.
- If the starting day is missing and the starting month is the same as the randomization month, then the starting day will be imputed to the randomization day and the medication will be assumed to be treatment emergent.
- If the starting month or year is missing, then the starting date will be imputed to the randomization date and the medication will be assumed to be treatment emergent.
- If the end day is missing, then the end day will be imputed to be the last day of the month.
- If the end month is missing and the end year is the same as the study termination year, then the event date will be set to missing and the patient will be assumed to be on the medication at time of study termination.
- If the end month is missing and the end year is before the year of study termination, then the end date will be imputed to the last day of the year (31DECXX).

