### **3. Study design and conduct**

#### **3.1. Study design**

This is a randomized, double-blind, 2-arm, parallel group study of approximately 274 evaluable patients designed to evaluate the safety and efficacy of histone deacetylase 6 (HDAC6) inhibitor ricolinostat for painful DPN. The study includes a 12-week randomized, double-blind, placebo-controlled treatment period in which patients will receive either ricolinostat or placebo, followed by a 12-week open-label safety extension period during which all patients will receive ricolinostat 120 mg daily.

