**Table 9. Estimand attribute for the key secondary endpoint of UENS at Week 12**

Estimand attribute	Description
Population	Full analysis set population, which consists of all patients who receive at least one dose of study drug and have baseline average pain intensity score and at least one post-baseline average pain intensity score.
Endpoint	Change from baseline in weekly mean of daily average pain based on the UENS at Week 12.
Intercurrent events	All values collected after treatment discontinuation will be included in the analysis. All missing values due to treatment or study discontinuation will be imputed using reference-based imputation with missing values imputed based on the placebo data. All other intermittent missing values will be imputed under the assumption of missing at random with each missing value imputed based on the treatment group assignment. This hypothetical scenario assumes that the treatment had no further benefit in patients that discontinued study medication while accounting for the disease trajectory and trial effect.
Summary measure	Difference between ricolinostat arm and placebo arm as measured by change from baseline in average pain at Week 12.

The analyses will follow those used for the primary efficacy analyses with a MMRM and multiple imputation as described in Section 7.

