### 8.2. Adjustment for multiplicity

If the significance level for the primary endpoint is statistically significant then each of the key secondary endpoints will be tested using a fixed sequence method with the following testing sequence:

- Change in mean average pain intensity from baseline to Week 4 as measured by the NRS.
- Change in non-pain neuropathic signs after 12 weeks in patients as assessed by change in the UENS.

Nominal p-values will be reported for all other analyses.

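### SAP Exhibit 4 gives Week 12 the Week 26 follow-up window, so no patient still on drug gets a Week 12 value for UENS or the other visit-based measures

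*SAP*

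**What the plan says.** - **The window.** In SAP Exhibit 4 the Week 12 row has target study day 84 and window "14 ≤ days after last dose ≤ 32". The Week 26 row (target Day 182) has the identical entry. All other post-baseline rows are bounded by study day.
- **How it is used.** SAP 6.1.4 bases analysis visits on derived study day because clinic visits can fall outside their planned windows. Study day and days after last dose are to be "compared to the target for each analysis visit as specified in Exhibit 4". The exhibit is titled "Example of study days and analysis timepoints", but it is the only window table. Last dose is not defined there.
- **The end of the double-blind period.** Footnote c states: "Week 8 is the end of the double-blind, placebo-controlled treatment period". SAP 3.1 states: "The study includes a 12-week randomized, double-blind, placebo-controlled treatment period".
- **The endpoints at stake.** Under SAP 8.2, if the primary succeeds, the key secondaries are "tested using a fixed sequence method with the following testing sequence": NRS at Week 4, then UENS at Week 12. For UENS, the text after SAP Table 9 says: "The analyses will follow those used for the primary efficacy analyses with a MMRM and multiple imputation as described in Section 7". For the other secondaries, SAP 6.1.5.3 says: "Missing values for secondary endpoints will not be imputed".
- **The schedule.** SAP Exhibit 3 and Protocol Table 1 place the Week 12 visit on Days 82-86. Under Protocol 9.6 all patients take daily ricolinostat from Week 12 to Week 24.

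**The concern.** A window counted from the last dose suits a follow-up visit after treatment has ended. It does not suit Week 12, where patients are still dosing daily and move directly into the open-label extension. Applied as written, the row rejects the visits it should capture.

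Week 12 is the only post-baseline UENS assessment in the double-blind period, and SAP 5.1 keeps later open-label data out of the first analysis. Literal programming would therefore leave the Week 12 UENS to imputation (SAP 6.1.5.2), with observed values only from any patients already off drug who happened to attend. BPI-SF, NTSS-6, Norfolk QOL-DN and PGIC are analysed as complete cases, so their Week 12 comparisons would lose every on-drug patient.

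The primary NRS endpoint is not at issue, because it is built from weekly means of diary entries. No effect on the safety summaries is claimed.

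**Working it through.** **Inputs.** Exhibit 4 windows; scheduled visit days from SAP Exhibit 3 and Protocol Table 1; daily dosing to Week 24 (Protocol 9.6); assessments by visit from Protocol 9.5 to 9.7.

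**1. Can the Week 12 window be derived from its own target?** Distance from target to each bound:

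- Weeks 2, 4, 8, 14, 18, 24 and 28: −4/+4 days (7 of 7). For example, Week 8 is 56 − 52 = 4 and 60 − 56 = 4.
- Week 1: 5 − 2 = 3 and 9 − 5 = 4.
- Week 12: no study-day bound is given, so the stated window cannot be obtained from Day 84. The ±4 pattern would give 80 to 88.

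**2. Does another row catch the visit?** The study-day windows are 2-9, 10-18, 24-32, 52-60, 94-102, 122-130, 164-172 and 192-200. Days 61-93 lie in none of them, so all five scheduled Week 12 days (82-86) are uncovered.

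**3. Does an on-drug Week 12 visit meet the stated window?** Days after last dose = visit day − day of last dose, and the result must lie between 14 and 32.

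- *Most recent dose.* Visit on Day 82, 83, 84, 85 or 86; last dose the same day or the day before. That is 5 × 2 = 10 combinations, each giving 0 or 1. None qualifies; the shortfall is 14 − 1 = 13 to 14 − 0 = 14 days.
- *Final dose of the study.* With that dose on Days 166-170, the difference runs from 82 − 170 = −88 to 86 − 166 = −80. None qualifies.
- *Last double-blind dose.* A last dose on Day 81 gives a window of 81 + 14 = 95 to 81 + 32 = 113; Day 84 gives 98 to 116; Day 86 gives 100 to 118. For last doses on Days 81-86 the only scheduled visit that can fall inside is Week 14 (Days 96-100). Week 12 (82-86) is too early and Week 18 (124-128) too late. Protocol 9.6.2 lists none of UENS, BPI-SF, NTSS-6, QOL-DN or PGIC at Week 14.

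**4. Who would qualify at Days 82-86?** The last dose must fall between 82 − 32 = Day 50 and 86 − 14 = Day 72, so only a patient who had already stopped drug.

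**5. What happens in the final database?** For a completer whose final dose is on Day 168, the window is 168 + 14 = Day 182 to 168 + 32 = Day 200. A Week 26 visit on Days 182-184 (14 to 16 days after the dose) then meets the Week 12 window. UENS and the four other measures are taken at Week 26, after both arms have received open-label ricolinostat. If all data were windowed together at the second lock, the rule could label these values as Week 12.

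**6. Does the proposed window work?** Days 80-88 contain all of Days 82-86, start after Week 8 ends (Day 60) and end before Week 14 begins (Day 94). Days 61-79 and 89-93 remain uncovered.

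**The case against.** The best reply is that this is one wrong cell which the rest of the SAP contradicts. Section 6.1.4 speaks of derived study day, 6.1.3 attributes post-baseline results by time from randomization, the row has the right target, and the exhibit calls itself an example. A Week 12 visit with almost no data would be conspicuous in the blinded data review of SAP 5.1, whose aims include assessing missing data and finalizing methods. Imputation with next to no observed values would probably fail visibly. UENS is formally tested only if the primary and the Week 4 NRS both succeed.

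Most of this stands as a reason to expect detection. It does not supply the missing bounds: someone would still have to choose a window. The protocol's visit range does not settle the matter, because SAP Section 1 makes the SAP govern where the two differ on analyses.

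On footnote c, the protocol itself lists the Week 12 visit under the Safety Extension, so naming Week 8 as the last double-blind visit follows that grouping, and the footnote assigns no data. That is fair. As worded, though, it still contradicts the 12-week period, and it is a supporting point only.

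The restriction to assessments before open-label dosing and the rule for make-up visits go beyond restoring the cell. The first is consistent with the data exclusion in SAP 5.1, although applying it on the day of the visit may need assessment and dosing times. The second is optional.

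**Conclusion.** The concern holds. Under each of the three readings of last dose, a patient on drug at Days 82-86 has no Week 12 analysis value for UENS, BPI-SF, NTSS-6, QOL-DN or PGIC at the first lock. The result is structural: 0 of 10 on-drug combinations qualify, with no dropout assumption. It rests on daily dosing up to the visit and on literal use of Exhibit 4. The documents give no dropout rate and schedule no return visit 14 to 32 days after stopping in the double-blind period, so the number of off-drug patients who might qualify cannot be estimated.

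The cause is very probably a copied row, and the blinded review may well catch it. It should still be treated as a must-fix item before unblinding, because the rule decides which observations enter a test under multiplicity control.

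**What to change.** - In Exhibit 4, replace the Week 12 window with 80 ≤ study day ≤ 88, limited to assessments made before the first open-label dose.
- Correct footnote c so that the double-blind period ends at Week 12, in agreement with SAP 3.1.
- Optionally, add a sentence saying whether a make-up in-clinic UENS on Days 61-79 or 89-93, before the first open-label dose, counts as Week 12. Protocol 13.2 makes UENS an in-clinic assessment and foresees unscheduled make-up visits.

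The cost is one table row, one footnote and, if wanted, one sentence in the SAP before unblinding. No new data, patients or procedures are needed. The programmer should check that assessment and dosing times are available for applying the pre-dose limit on the day of the visit.
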